8.10 Management of Cytokine Release Syndrome (CRS)

Every participant that is due to receive the TR006 infusion will receive a dose of paracetamol and chlorphenamine maleate 30 minutes before the infusion.

The dosing schedules (Table 11 and

Table 12) are included below (adapted from British National Formulary for Children - BNFC) and willalso be prescribed on the child's local medical electronic chart to give (as required) after pre-medication to manage any symptoms. [41] [42]

Table 11: Paracetamol Pre-medication Regime:

Age Range of child	Dose of Paracetamol (Can be given every 4-6 hours, max 4 doses per day)
6-23 months	120 mg
2-3 years	180 mg
4-5 years	240 mg
6-7 years	240-250 mg
8-9 years	360- 375 mg
10-11 years	480- 500 mg
12-15 years	480-750 mg
16-17 years	0.5- 1 g

Table 12: Chlorphenamine Pre-medication Regime:

Age Range of child	Dose of Chlorphenamine
1-23 months	1mg up to twice daily
2- 5 years	1mg every 4-6 hours
6- 11 years	2 mg every 4-6 hours
12-17 years	4 mg every 4-6 hours

Continuous monitoring and clinical checking of the patient during and immediately after the TR006 infusion will be carried out during the Baseline Day 0 visit. Clinical status updates and management will be discussed and coordinated between the study team (delegated clinicians, physicians and the Chief Investigator) as well as with the on-call, on-site clinical teams at Great Ormond Street Hospital.

The following clinical features may alert the study team of possible CRS:

- Fever usually persistent > 38°C.
- Hypotension: Assessed relative to baseline values (may be systolic or isolated diastolic causing widening of pulse pressure.
- Hypoxia.
- Rash.
- Coagulopathy.
- Organ dysfunction including cardiac, renal, hepatic or respiratory.
- Derangement in vital signs (for example: increased heart rate, respiratory rate and/or elevated PEWS score).

Investigations to be considered if CRS is suspected (and further may be considered as clinically indicated):

- Haematology profile (including Full Blood Count and blood film).
- Coagulation profile (including D dimers and fibrinogen).
- Serum biochemistry (including renal, liver, bone profile).
- CRP.
- Ferritin.
- Blood, urine and stool cultures.
- Nasopharyngeal aspirate for bacteria and viruses.
- Chest X-ray / CT chest.
- Transthoracic echocardiogram.
- Daily assessment of neurological and cognitive function with Glasgow Coma Scale, gait assessment and age appropriate cognitive test (if possible).
- Cytokine analysis (if feasible: ideally at onset of CRS symptoms and one week after).

The study team may maintain close liaison with the Critical Care Outreach Team for further clinical support if required.

On suspicion of CRS, features will be graded according to Common Terminology Criteria for Adverse Events (CTCAE) grading system (Table 13) as shown below: [37]

Table 13: Chlorphenamine Pre-medication Regime:

Immune system disorders						
CTCAE Term	Grade 1	Grade 2	Grade 3	Grade 4	Grade 5	
Cytokine release syndrome	Fever with or without	Hypotension responding to	Hypotension managed with	Life-threatening	Death	
	constitutional symptoms	fluids; hypoxia responding to	one pressor; hypoxia requiring	consequences; urgent		
		<40% O2	≥ 40% O2	intervention indicated		
Definition: A disorder characterized by fever, tachypnea, headache, tachycardia, hypotension, rash, and/or hypoxia caused by the release of cytokines.						
Navigational Note: Also consider reporting other organ dysfunctions including neurological toxicities such as: Psychiatric disorders: Hallucinations or Confusion; Nervous system						
disorders: Seizure, Dysphasia, Tre	emor, or Headache					

Based on the severity of the clinical features during presentation, assessment and treatment for CRS will be initiated as follows (Table 14):

CRS Grade	Symptom or Sign	Management			
1	Persistent fever with or without constitutional symptoms.	 Paracetamol for fever. Ibuprofen 2nd line if not contraindicated. Assess for infection with blood and urine cultures and chest x-ray. Empiric broad spectrum antibiotics to cover for infection. Maintenance IV fluids for hydration if patient unable to meet this requirement orally. Symptomatic treatment of constitutional symptoms, as required. 			
2	Hypotension. (Consider if >20% drop in systolic or diastolic reading from baseline)	 IV fluid bolus with 10-20ml/kg of normal saline (0.9% sodium chloride). Can give further fluid bolus if BP remains low. Consider IV tocilizumab (anti-IL6 therapy)* for the treatment of hypotension that is refractory to IV fluid boluses. Early involvement of Critical Care Outreach Team. If hypotension persists despite IV fluid boluses and anti IL6 therapy: Perform transthoracic echocardiogram and start vasopressors with consideration of more invasive methods of haemodynamic monitoring. If hypotension persists beyond 24 hours of anti-IL6 therapy: consider starting IV methylprednisolone* and continue until symptoms have improved (for example: Grade 1 CRS or below; after which dose can be tapered over 3 days). Manage fever and constitutional symptoms as in Grade 1 CRS. 			
	Hypoxia Need oxygen to maintain saturations >90%	Supplementary oxygen via nasal cannula (low flow up to 6L/min) or facemask (high flow).			
	Organ toxicities	Symptomatic management as required clinically as per standard guidelines depending on system affected.			
3	Hypotension	 IV fluid boluses as indicated for Grade 2 CRS. Early involvement of Critical Care Outreach Team. 			

	Нурохіа	 Consider IV tocilizumab* as for Grade 2 CRS (if not already initiated). Vasopressors, as needed. If hypotension persists despite IV fluid boluses and anti-IL6 therapy, consider transfer to intensive care, perform transthoracic echocardiogram, start vasopressors and initiate methods of invasive haemodynamic monitoring. Close monitoring of patients receiving IV fluid boluses with strict monitoring input and output fluid balance. Repeat boluses may be considered if no improvement of blood pressure or signs of poor peripheral perfusion (e.g. capillary refill time >2 seconds or urine output <1ml/kg/hour). If no response to 2 doses of tocilizumab: consider initiating IV methylprednisolone⁺ and continue until symptoms have improved and when they are Grade 1 CRS or below, dose can be tapered over 3 days. Manage fever and constitutional symptoms as in Grade 1 CRS.
	Organ toxicities	ventilation). Symptomatic management as required clinically as per standard
		guidelines depending on system affected.
4	Hypotension	 IV fluids, consider anti IL6 therapy, inotropic support and transfer to intensive care. Echocardiogram and initiate invasive haemodynamic monitoring as in CRS Grade 3. IV methylprednisolone⁺ to start if no response to IV tocilizumab: Continue until symptoms are Grade 1 CRS or below, after which dose can be tapered over 3 days. For life threatening or CRS that is unresponsive to the measures given above: Higher doses of corticosteroids may be considered e.g. IV Methylprednisolone 10mg/Kg as well as further therapies as guided by the transplant, intensive care and specialist immunology teams.
	πγμυχια	supplementary oxygen delivery.
	Organ toxicities	Symptomatic management as required clinically, as per standard guidelines depending on system affected.

*Intravenous tocilizumab (anti IL6 therapy) dose for children with body weight up to 30kg: 12mg/kg (max per dose 800mg) and IV Tocilizumab dose for bodyweight >30kg: 8mg/kg (max per dose 800mg). Doses can be repeated up to 3 times a day. *Intravenous methylprednisolone: Initial dose 2mg/kg followed by 1mg/kg IV twice a day.

Equivalent doses of other corticosteroids (eg dexamethasone) may be used if associated neurotoxicity. Dexamethasone 10mg IV stat (or 1mg/kg for children under 10 kg) followed by Dexamethasone 6mg IV (or 0.5mg/kg for children under 10 kg) if associated neurotoxicity.

Triggers for urgent intensive care transfer:

If CRS is suspected, the above are guidelines only and the study team will discuss the participant's case with the on-call Paediatric Intensive Care Consultant and the Immunology Lab to guide monitoring and further treatment for each individual case. The following should be considered key triggering factors for the transfer of the patient to intensive care:

- Hypotension refractory to fluid boluses whether or not Tocilizumab has been commenced.
- Oxygen requirement >6L/min (approximately 40% FIO2).
- Need for other organ support (such as renal failure).

8.11 Non-Investigational Medicinal Products (NIMPs)

Medications that will be given as prophylaxis prior to TR006 administration are commercially available and routinely prescribed to prevent potential infusion reactions. All participants will be given the following medications prior to infusion:

- Chlorphenamine or equivalent anti-histamine, administered orally (See
- Table 12).
- Paracetamol, administered orally (See Table 11).
- The Trust guidelines/Ward SOPs will be followed in the event of a cytokine release syndrome (CRS) for participants dosed with TR006 in Walrus Ward (See Section 8.10 Management of Cytokine Release Syndrome (CRS)).

The above medications will be prescribed in line with the British National Formulary for Children (BNFC) at doses appropriate to the patient's age and/or weight. These medications are designated as NIMPs (Non-Investigational Medicinal Products). They will be dispensed from the Trust pharmacy stock and according to the local hospital guidelines. All the above have marketing authorisation and are routinely used in accordance with their license.

8.12 Participant Withdrawal Criteria

Participants have the right to withdraw from the study at any time for any reason. The investigator also has the right to withdraw patients from the study in the event of inter-current illness, AEs, SAE's, SUSAR's, protocol violations, cure, administrative reasons or any other reasons deemed appropriate. It is understood by all concerned that an excessive rate of withdrawals can render the study un-interpretable; therefore, unnecessary withdrawal of patients should be avoided. Should a patient decide to withdraw from the study, all efforts will be made to report the reason for withdrawal as thoroughly as possible.

As the IMP in this trial is an advanced therapy with a single infusion, participants who wish to withdraw from trial after IMP has been administered, will be asked to confirm whether they are still willing to attend the safety follow up visits as per protocol for the duration of the trial. If participants are not willing to do this, consent will be sought for the trial team to access routine data collected from hospital/GP visits for the duration of the safety follow up period.

In situations where a patient has to be withdrawn or decides to withdraw from the study, an additional patient may be recruited and dosed if:

- They withdraw prior to the TR006 infusion.
- They withdraw during their 4-week follow-up period, and have not yet experienced a DLT.

If a patient withdraws from the trial a withdrawal form in the study database will be completed.

The DMC will review all patients, including any withdrawn patients, to determine if a primary outcome has occurred (DLT, no DLT or DLT not determined in the active period).

In the following situations, the withdrawn patient will have contributed to the primary outcome and no additional patient will be recruited:

- If they withdrew after they completed their 4-week follow-up safety period.
- If they experience a DLT during their 4-week follow-up safety period, which may or may not be the reason for withdrawal.

9 Assessment of Safety

Definitions

9.1.1 Adverse event

Any untoward medical occurrence in a patient or clinical trial subject administered a medicinal product and which does not necessarily have a causal relationship with this treatment.

An adverse event can therefore be any unfavourable and unintended sign (including an abnormal laboratory finding), symptom, or disease temporally associated with the use of an investigational medicinal product, whether or not considered related to the investigational medicinal product.

9.1.2 Adverse Reaction (AR) of an Investigational Medicinal Product

An untoward and unintended response in a participant to an investigational medicinal product which is related to any dose administered to that participant.

The phrase "response to an investigational medicinal product" means that a causal relationship between a trial medication and an AE is at least a reasonable possibility, i.e. the relationship cannot be ruled out.

All cases judged by either the reporting medically qualified professional or the Sponsor as having a reasonable suspected causal relationship to the trial medication qualify as adverse reactions.

9.1.3 Serious Adverse Event or Serious Adverse Reaction

A serious adverse event is any untoward medical occurrence that:

- results in death.
- is life-threatening.
- requires inpatient hospitalisation or prolongation of existing hospitalization.
- results in persistent or significant disability/incapacity.
- consists of a congenital anomaly or birth defect.

Other 'important medical events' may also be considered serious if they jeopardise the participant or require an intervention to prevent one of the above consequences.

NOTE: The term "life-threatening" in the definition of "serious" refers to an event in which the participant was at risk of death at the time of the event; it does not refer to an event which hypothetically might have caused death if it were more severe.

9.1.4 Serious Adverse Reaction (SAR)

An adverse event that is both serious and, in the opinion of the reporting Investigator, believed with reasonable probability to be due to one of the trial treatments, based on the information provided.

9.1.5 Suspected Unexpected Serious Adverse Reaction (SUSAR)

A serious adverse reaction, the nature and severity of which is not consistent with the information about the medicinal product in question set out:

- in the case of a product with a marketing authorisation, in the summary of product characteristics (SmPC) for that product.
- in the case of any other investigational medicinal product, in the investigator's brochure (IB) relating to the trial in question.

9.1.6 Important Medical Events (IME) & Pregnancy

These are defined as medical events that may not be immediately life-threatening or result in death or hospitalisation but may jeopardise the participant or may require intervention to prevent one of the other outcomes listed in the definitions above (in Section 9.1.3 Serious Adverse Event or Serious Adverse Reaction) and such medical events should also be considered serious.

Although not a Serious Adverse Event, any unplanned pregnancy will also be reported via the SAE reporting system (as listed in Section 9.4 Reporting Procedures for Serious Adverse Events). Pregnancy reporting includes pregnancy of a female participant or a female partner of a male participant. Should a trial participant become pregnant during the trial or female partners of male participants who become pregnant, she will be followed up for safety until the birth of the child or until Safety Follow-up Month 24 (whichever is latest).

9.2 Expected Adverse Drug Reactions and Serious Adverse Events

As TR006 has never been tested in humans before, there is currently no available list of medical events/reactions that are expected for the ATIMP. Hence any serious adverse events that are deemed related to the ATIMP (SARs) will be considered SUSARs.

9.3 Recording and evaluation of adverse events

AEs (including SAEs) will be recorded from the Screening Visit to Month 12 visit. From Month 12-24 safety follow-up period, only SUSARs will be reported.

As stated in Section 5.1, DLTs will be assessed from week 0 to week 4 of the study.

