3.2 Objectives and endpoints

Objectives	Outcome Measures/Endpoints
Primary Objective: To determine safety and optimal tolerated dose of TR006 to prevent CAV in paediatric heart	Primary Endpoint: Occurrence and nature of Dose-Limiting Toxicities (DLTs) occurring within 4 weeks post-
transplant patients in a phase I study.	infusion of the expanded autologous thymus derived Treg product (ATIMP).
Secondary Objectives:	Secondary Endpoints:
1. To assess the feasibility of generating TR006 in the Good Manufacturing Practice facility.	Amount of TR006 manufactured per patient.
2. To investigate the clinical and immunological	Assessment of Immunological response:
responses to TR006 in paediatric heart	• Frequency of circulating leukocyte subsets.
transplant patients.	• Quantity of alloantigen-specific conventional T cells, Tregs and CD8+.
	 Presence of anti-HLA to evaluate tissue infiltrating cells.
	Assessment of clinical response:
	• Diagnosis of CAV as measured by coronary angiography within 24 months post-infusion of TR006.
	 Graft loss as measured by inclusion of patient on the re-transplant waiting list through rejection (acute or chronic) within
	24 months post-infusion of TR006.
	• Recipient mortality within 24 months post- infusion of TR006.
	 Acute graft rejection as measured by endomyocardial biopsy (EMB) within 24 months post-infusion of TR006.
	• Antibody-mediated rejection as measured by development of donor specific antibodies within 24 months post-infusion of TR006.

r	
	 Infection related rehospitalisation events within 24 months post-infusion of TR006.
	 (Cardiac function) Left ventricular ejection fraction as measured by echocardiography monthly for 12 months and at 24 months post-infusion of TR006.
	 (Renal function) Mean calculated GFR at 24months post-infusion of TR006.
	• Description of non-DLT adverse events and those occurring beyond week 4 and up to 24 months post-infusion of TR006.
	 Immunosuppressive doses at 12 and 24 months post-infusion of TR006.
3. To assess the feasibility of retaining participants for the duration of the study and completion of study visits and assessments	Number of study visits completed per participant.
	 Responses to items in questionnaires or surveys exploring the study and treatment experience of the participants and their parents/guardians.

4 Assessment and Management of Risk

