4.2.4 Malignancy

Malignant disease after treatment with thymus-derived (Treg) cell product could, in principle, arise either as a consequence of transferring neoplastic cells or as a consequence of transferred cells promoting the growth of spontaneous tumours. Neoplastic cells within the cell product might arise during in vitro culture or after transfer into the recipient. Further, the infused regulatory T population might suppress immune responses against malignant cells. Although no long-term data on this aspect of Treg therapy are available, those that have been published did not report safety concerns of this type. Furthermore, the cell dose that will be infused represents approximately 2% of the patient's endogenous regulatory T cell population suggesting that an impact on malignancy will be small.

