- Doctor review (including physical examination).
- Vital signs.
- Height and weight.
- ECG (12-Lead).
- Echocardiography.
- Intravascular ultrasound (only for children over 25kg).
- Coronary angiography (only for children over 25kg).
- Clinical blood tests (Full blood count, liver profile, renal profile, LDH, EBV, CMV viral load and HLA antibody testing (includes panel reactive antibodies and donor specific antibodies)).
- Urine pregnancy test (if applicable).
- Translational research blood samples.

Safety Follow-up: Month 12 post TR006 infusion. (+/- 4 weeks)

- Concomitant medication collection.
- Adverse Events collection.
- Doctor review (including physical examination).
- Vital signs.

- Height and weight.
- ECG (12-Lead).
- Echocardiography.
- Clinical blood tests (Full blood count, liver profile, renal profile, LDH, EBV and CMV viral load).
- Translational research blood samples.

End of Study: Month 24 post TR006 infusion. (+/- 4 weeks)

- Concomitant medication collection.
- Adverse Events collection.
- Doctor review (including physical examination).
- Vital signs.
- Height and weight.
- ECG (12-Lead).
- Echocardiography.
- Clinical blood tests (Full blood count, liver profile, renal profile, LDH, EBV, CMV viral load and HLA antibody testing (includes panel reactive antibodies and donor specific antibodies)).
- Urine pregnancy test (if applicable).
- Translational research blood samples.

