9.4 Reporting Procedures for Serious Adverse Events

All SAEs (other than those defined in the protocol as not requiring reporting) must be reported on the SAE reporting form to R&D within 24 hours of the Site Study Team becoming aware of the event. The event will be recorded in the sponsor's SAE form (F44) and emailed to [contact] or faxed to the Joint R&D office ([name]) within the reporting timelines. R&D will perform an initial check of the report, request any additional information if required. Additional and further requested information (follow-up or corrections to the original case) will be detailed on a new SAE Report Form and faxed/emailed to R&D.

AEs (including SAEs) will be recorded from the Screening Visit to Month 12 visit. From Month 12-24 safety follow-up period, only SUSARs will be reported.

As stated in Section 5.1, DLTs will be assessed from Week 0 to Week 4 of the study.

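### Sections 9.3 and 9.4 end adverse event recording at Month 12, contradicting the 24-month adverse event endpoint and the Month 24 adverse event collection in the schedule

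*Protocol*

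**What the plan says.** **Endpoints.** Section 3.2 of the protocol lists, under clinical response, "Description of non-DLT adverse events and those occurring beyond week 4 and up to 24 months post-infusion of TR006". It separately lists "Infection related rehospitalisation events within 24 months post-infusion of TR006". Mortality, graft loss, acute rejection and antibody-mediated rejection are further endpoints with the same 24-month horizon.

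**Recording rule.** Sections 9.3 and 9.4 give the same rule twice: "AEs (including SAEs) will be recorded from the Screening Visit to Month 12 visit", followed by "From Month 12-24 safety follow-up period, only SUSARs will be reported".

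**Visit schedule.** Section 7.5 has a final visit headed "End of Study: Month 24 post TR006 infusion. (+/- 4 weeks)", and its list includes "Adverse Events collection". Table 5 marks adverse event review at Month 24, and Table 16 names Month 24 in its adverse event row. Section 4 gives the purpose of that visit as detecting delayed or chronic complications.

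**Related provisions.** Section 9.1.3 makes an event serious if, among other criteria, it "requires inpatient hospitalisation or prolongation of existing hospitalization". Sections 8.8 and 9.2 treat every serious event judged related to TR006 as a SUSAR. Section 7.11 follows SAEs until 30 days after the last participant's final visit, or until they resolve.

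**The concern.** An endpoint defined to Month 24 needs a recording rule that runs to Month 24. Sections 9.3 and 9.4 instead narrow the second year to events that are serious, judged related to the product and unexpected. Because all related serious events count as unexpected here, the working filter is seriousness plus causality.

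That filter matters in this population. Participants stay on tacrolimus and mycophenolate (Section 4.3), and Section 1.1 links immunosuppressive drugs to infection, viral reactivation and lymphoproliferative disease. A competing explanation for a late infection will often be at hand. In an open-label trial the causality judgement is made by people who know the dose and the hypothesis. A table of adverse events to 24 months built on this rule would show fewer events in year 2 than occurred, and a reader could take absence of recording for absence of harm.

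Late harm is one reason for a second year. Section 4.2.4 concedes, on malignancy, that "no long-term data on this aspect of Treg therapy are available", though it adds that published reports raised no concern of this type. With 9 to 12 participants, one unrecorded late event can alter the description. A statistical analysis plan cannot repair this, because it cannot analyse what the case report form did not collect.

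**Working it through.** The plan states no figure to reproduce for this point. The check sets the passages side by side and then works out how much follow-up time is affected.

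**Step 1: which rule applies in Months 12 to 24**

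| Place in protocol | Months 12 to 24 |
|---|---|
| 3.2, adverse event endpoint | Adverse events described to Month 24, with no limit on seriousness or causality |
| 3.2, infection rehospitalisation | Events counted to Month 24 |
| 7.5, Table 5, Table 16 | Adverse event collection at the Month 24 visit |
| 9.3 and 9.4 | Recording ends at Month 12; SUSARs only afterwards |
| 7.11 | SAEs followed up to the end of the trial; no statement that new SAEs are recorded after Month 12 |

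The first three rows agree with each other, and 9.3 and 9.4 contradict them. Section 7.11 does not settle it, because following up a known event is different from recording a new one.

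**Step 2: what falls outside 9.3 and 9.4 in year 2**

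- Non-serious adverse events: not recorded.
- Serious events judged unrelated: not recorded.
- Serious events judged related: still reported, as SUSARs.
- Infection admissions: serious by the hospitalisation criterion, so not recorded as SAEs when judged unrelated, unless captured separately for their own endpoint. The Month 24 list in Section 7.5 has no item specific to rehospitalisation.

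**Step 3: share of follow-up time**

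Inputs: follow-up 24 months (Section 7.9); cut-off at Month 12 (9.3, 9.4); Month 12 window of plus or minus 4 weeks (7.5); endpoint starting after week 4 (3.2); 9 participants, up to 12 (5.1). Four weeks = 28 / 30.4375 = 0.92 months.

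- Share of all follow-up: (24 − 12) / 24 = 50%.
- Week 4 to Month 24 window: 24 − 0.92 = 23.08 months. Affected share: 12 / 23.08 = 52%.
- Month 12 visit 4 weeks early (11.08): (24 − 11.08) / 23.08 = 12.92 / 23.08 = 56%.
- Month 12 visit 4 weeks late (12.92): (24 − 12.92) / 23.08 = 11.08 / 23.08 = 48%.
- Participant-months with complete follow-up: 9 × 12 = 108 of 9 × 23.08 ≈ 208; for 12 participants, 12 × 12 = 144 of 12 × 23.08 ≈ 277.

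If recording ran to Month 24, the affected share would fall to zero.

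**The case against.** The strongest reply is that the protocol does not uniformly stop collection at Month 12. If sites follow the schedule, adverse events are collected at Month 24 and the endpoint can be reported. This stands, and it is why the defect is a contradiction and not a proven loss of data. A reader might infer that the 24-month safety data cannot be delivered; the documents do not support that. Even so, Month 24 is the only scheduled visit after Month 12, so the schedule alone would gather a year of events retrospectively.

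Second, a reader might infer that late rejection, graft loss or death would go unrecorded. They are separate 24-month endpoints in Section 3.2, and nothing says they are captured only through the adverse event log. Section 12.1 also allows a committee meeting on the death of any infused patient, with no Month 12 limit. This objection stands in full. For infection rehospitalisation it stands only if a separate capture route exists, and the protocol names none.

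Third, the causality filter may be mild. Section 9.1.2 counts an event as related when a link cannot be ruled out, as judged by either the reporter or the sponsor. On that threshold a late malignancy could well be reported. Section 9.1.4 uses a stricter standard of reasonable probability in the reporting investigator's opinion, so the strength of the filter is uncertain. It still excludes unrelated serious events and all non-serious ones.

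Fourth, one half is a share of calendar time, not of safety data. Laboratory tests, echocardiography and donor-specific antibody testing continue at Month 24, and SUSARs remain reportable. This also stands.

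**Conclusion.** The contradiction is real and sits in current protocol text: 9.3 and 9.4 against 3.2, 7.5, Table 5 and Table 16. If 9.3 and 9.4 are followed, non-serious adverse events and serious events judged unrelated go unrecorded for 12 of 24 months, or 52% of the week 4 to Month 24 window (48% to 56% across the Month 12 visit window). The 24-month adverse event description would then be biased low and filtered on causality. The number of missed events cannot be stated, because the protocol gives no event rates.

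This rests on a literal reading of 9.3 and 9.4 and on full follow-up for the participant-month figures. The effect on infection rehospitalisation depends further on there being no separate capture route.

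The primary endpoint and the dose-escalation decisions close at 4 weeks and are untouched. This should be fixed, ideally before the case report form is final, but it does not undermine the trial's main question.

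**What to change.** Reconcile the passages in one of two ways.

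1. **Preferred.** Amend 9.3 and 9.4 so that at least all SAEs, and all events that are Section 3.2 endpoints, are recorded to the Month 24 visit regardless of causality. If non-serious events are to stop at Month 12, limit the 3.2 adverse event endpoint after Month 12 to serious events and have Section 7.5 and Tables 5 and 16 say so.
2. **Otherwise.** Restate the 3.2 adverse event endpoint as running to Month 12, state how infection rehospitalisations are captured to Month 24, and align Section 7.5 and Tables 5 and 16 with the shorter window.

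The first option costs protocol wording, a case report form setting and a little extra data entry for 9 to 12 participants; the Month 24 visit and its adverse event review already exist. The second saves that data entry but gives up the second-year adverse event description.
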